7.11 TREATMENT OF OVERDOSE

In the event of an overt overdose, with or without adverse event, the investigator should:

- Contact the sponsor immediately via Stragen Services using the SAE/AESI/pregnancy/overdose form,
- Closely monitor the participant for any AE/SAE and laboratory abnormalities as appropriate and provide supportive care as necessary,
- Document the quantity of the excess dose in the eCRF.

Decisions regarding treatment interruptions or modifications will be made by the investigator, in consultation with the sponsor, based on the clinical evaluation of the patient.

8. STATISTICS

8.1 STATISTICAL AND ANALYTICAL METHODS

8.1.1 General statistical considerations

Statistical analyses will be performed by the sponsor or under the supervision of the sponsor and further detailed in the SAP, which will be finalised prior to the unblinding of data and database lock.

In general, summary tabulations will be presented by treatment arm and will display the number of observations, mean, standard deviation (SD), median, Q1, Q3 quartiles, minimum, and maximum for continuous variables, and the number and percent per category for categorical data.

Patient disposition

An accounting of study patients by disposition will be tabulated and the number of patients in each analysis set will be summarised. Patients who discontinue study treatment and patients who withdraw from the study, with associated reason(s), will be summarised. A summary of protocol deviations by treatment arm and the corresponding listing by patient will be generated.

Nominal alpha level of significance

Unless otherwise noted, as the trial is a safety trial and an estimation efficacy study and not powered for efficacy endpoints, all tests performed on efficacy assessments will be conducted at a 1-sided nominal alpha level of 0.10 and confidence intervals (CIs) will be calculated at 80%, 2-sided 95% confidence intervals will also be provided.

Missing data handling

As a general rule, missing data will not be replaced. Sensitivity analyses based on multiple imputation will be proposed and further detailed in the SAP.

Multiplicity

As it is mainly an estimation trial, there is no adjustment for multiplicity.

8.1.2 Sample size

The minimum required sample size for this study has been estimated at 42 evaluable patients. Since it is an exploratory safety study, it has not been based on a formal sample size calculation. However, with regard to the primary safety endpoint, it is worth noting that 28 patients enrolled in the IFB-088 arm will be sufficient to observe at least one SAE which incidence is greater than or equal to 5% (10% resp.) with a probability of at least 76.2% (94.8% respectively). In addition, 42 patients are also considered sufficient to observe some numerical efficacy signal on some key parameters. Assuming a 15% drop-out rate, 50 patients will be randomised.

8.1.3 Analysis Sets

The following analysis sets will be considered. Additional details of analysis sets of patients may be defined in the SAP.

- Safety set (SS): randomised patients having received at least one dose of the IMPs and analysed according to the treatment actually received,

- Efficacy sets:

- Randomised set (RS): all patients “as randomised” (i.e. according to the treatment group to which they were randomised, regardless of the treatment actually taken),
- Full analysis set (FAS): as randomised patients having received at least one dose of the IMPs and having a non-missing baseline value,
- Per protocol set (PPS):

FAS patients fulfilling the following criteria. Criteria definition will be further detailed during a blinded data review meeting and specified in the SAP:

- Major inclusion/exclusion criteria satisfied,
- Absence of relevant protocol violations likely to affect treatment efficacy,
- Adequate study medication compliance, defined as intake of at least 80% of the planned total dose.

8.1.4 Population and baseline characteristics description

Demographics, concomitant medications, and other baseline characteristics will be described by treatment arm according to general considerations. Details will be provided in the SAP.

8.1.5 Efficacy / safety analysis

8.1.5.1 Primary outcome

Usual descriptive statistics will be used and detailed in the SAP to analyse the safety parameters.

AEs will be classified by system organ class and preferred term using the Medical Dictionary for Regulatory Activities (MedDRA). AEs will be listed and summarised by, MedDRA preferred term, severity, and relationship to study drug. In the event of multiple occurrences of the same AE with the same preferred term in one patient, the AE will be counted once as the occurrence.

8.1.5.2 Secondary outcomes

Efficacy endpoints

Analyses will be further detailed in the SAP.

The analysis of efficacy endpoints will be primarily performed in the FAS. A secondary analysis will be proposed in the PPS.

- Change in ALSFRS-R score: from baseline to 6 months will be analysed using a mixed model for repeated measures (MMRM) assuming missing at random (MAR) and unstructured covariance matrix and including fixed factors for treatment, visit (categorical variable), treatment-by-visit interaction, random patient factor and baseline ALSFRS-R as a continuous covariate. The degrees of freedom will be estimated using the Kenward-Roger's approximation. Least square means (LSMs) of change from baseline and LSM differences in change from baseline between active doses and placebo will be presented along with 80% and 95% CIs and the comparison p-value. A one-sided nominal significance level of 0.10 will be used for treatment comparison. Model assumptions will be checked (plot of studentized residuals vs predicted values, etc.). If the model assumptions do not hold, a rank

semi-parametric analysis of covariance (ANCOVA) model (or a rank non-parametric Quade's ANCOVA model if the assumptions of this latter do still not hold) will be proposed instead. As the MAR assumption is untestable and may not hold for subjects withdrawing at their own will, a sensitivity analysis will be based on a pattern mixture model that uses a multiple imputation technique analysed with an ANCOVA with pre specified fixed factors and covariates. The imputation model will be further clarified in the SAP. Another sensitivity Bayesian analysis using the historical placebo data from the ProMISe study [26] will be also performed and further detailed in the SAP. An intrapatient analysis of ALSFRS changes will be performed.

- Worsening (i.e. progression to a higher stage at 6 months compared to the baseline stage defined by ALS-MITOS score): the proportion of progressors will be compared between both treatment groups. The difference in binomial proportions will be estimated along with an exact 95% CI. A sensitivity Bayesian analysis using the historical placebo data from the ProMISe study [26] will be also performed and further detailed in the SAP. Progressors will also be analysed in a logistic regression model adjusting for treatment and additional relevant covariates (specified in the SAP). The treatment effect will be estimated in terms of an odds ratio associated with the 95% CI and p-value and also in terms of a difference in progression rates with its 95% CI using the method proposed by Ge and al. [45].
- Change in King's College score: the endpoint will be analysed with an approach similar to the analysis of ALS-MITOS score.

Analyses of the changes in efficacy endpoints from baseline to month 3 (as inferential analysis) and from month 3 to month 6 (as descriptive analysis) will be also proposed and further detailed in the SAP.

- Respiratory function: changes from baseline to 3 months and from baseline to 6 months will be analysed. Analyses will be further detailed in the SAP.
- Bioelectrical analysis: changes from baseline to 3 months and from baseline to 6 months will be analysed for the planned following parameters: phase angle, Z200/Z5 impedance ratio, skeletal muscle mass, dry mass, and dry mass without fat. Analyses will be further detailed in the SAP.

PK Analysis

Individual plasma concentrations of IFB-088 and IFB-139 (i.e. IFB-088 metabolite) with corresponding nominal sampling times, will be tabulated for each subject and scheduled sampling time, together with descriptive statistics. Mean plasma IFB-088 concentrations profiles by cohort will be presented over time graphically, using blood sampling time (x axis) and concentrations (y axis) on both linear and semi-log scales.

Derived and observed PK parameters will be evaluated by noncompartmental analysis. The following parameters will be listed and summarised by cohort, as appropriate:

- AUC, ng.h/mL,
- C_{max}, ng/mL, with associated T_{max}, h,

- Terminal or apparent terminal $t_{1/2}$, h,
- Apparent systemic clearance (Cl/F, L/h) and apparent volume of distribution (Vd/F, L) at steady state, where F is the overall oral bioavailability of IFB-088.

For the calculation of derived PK parameters, concentrations below the lower limit of quantification (LLOQ) will be assigned a value of zero.

Plasma concentrations of IFB-088 will also be analysed using a population PK modelling approach to develop a population PK model in patients with ALS. Results of this model will be used to estimate PK parameters and variability in patients and simulate new dosing schemes (with AUC and C_{max} information) to help choosing the doses for subsequent clinical studies.

Based on our previous PK analyses (Phase I), the developed population pharmacokinetics (popPK) model with plasma concentrations and urine data of IFB-088 and IFB-139 in patients (P188_MAD/PK/2019-001) will be evaluated. To evaluate the predictive performance of the model, goodness-of-fit plots for the predicted and the observed concentration will be first inspected. Then, prediction error (PE) will be calculated to assess the predictive performance of the model. Model bias will be determined with the mean prediction error (MPE) and the median prediction error (MDPE). Model imprecision will be determined with the mean absolute error (MAE) and the median absolute prediction error (MDAPE). This evaluation will be performed using a non-linear mixed effects model with NONMEM software (ICON Development Solutions v7.5). The R software v4.4.1 will be used for goodness-of-fit diagnostics and graphical displays. Then, this model will be optimised and used to estimate PK parameters and variability in patients (CL/F, V/F, $T_{1/2}$ and AUC), and simulated optimal dosing schemes.

A PK/PD (pharmacokinetic/pharmacodynamic) model could be developed according to the available data. The population PD analysis will be performed with a sequential method using the final PK model. In a first step, the PK/PD of each PD data will be fitted separately to define the model more easily then the run simultaneously estimated PD parameters of each PD data.

PK and PD data will be listed and presented in graphical and/or tabular form as appropriate to the data, and will be summarised descriptively.

Analysis of changes in potential biomarkers

Details of analysis will be provided in the SAP.

Changes in plasma concentration of TDP-43, NfL heavy chain and NfL light chain will be measured from baseline to 6 months.

Changes in plasma concentration of inflammatory and oxidative stress biomarkers will be measured from baseline to 3 months, and from baseline to 6 months. All changes will be compared between both arms.

Correlation of biomarkers with clinical endpoints will be assessed.

QoL endpoint

Change in ALS-AQ40 QoL scores from baseline will be assessed at 6 months and compared between both arms.

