	
which the patient is randomized. Imputed values will be rounded to the nearest integer. Imputed value higher than 48 will be replaced by 48 and imputed value lower than 0 will be replaced by 0.
 
 - Missing data due to drop-outs or withdrawal will be imputed with the same approach used for handling missing data due to deaths for reasons not related to disease progression. Imputed values will be rounded to the nearest integer. Imputed value higher than 48 will be replaced by 48 and imputed value lower than 0 will be replaced by 0. • Estimand #2: Missing data will be handled depending on the type of the intercurrent event (i.e.). 
 - Missing data due to deaths, whatever the cause: the ALSFRS-R score at month 6 will be imputed by the worst value (i.e. 0). - Missing data due to drop-outs or withdrawal will be imputed with the same approach as for Estimand #1 used for handling missing data due to deaths not related to disease progression. Imputed values will be rounded to the nearest integer. Imputed value higher than 48 will be replaced by 48 and imputed value lower than 0 will be replaced by 0. • Estimand #3: Missing data will be handled depending on the type of the intercurrent event (i.e.). 
 -Missing data due to death whatever the cause: the ALSFRS-R score at month 6
--	--

STATISTICAL ANALYSIS PLAN		
InFlectis BioScience	Sponsor: Protocol Number:	InFlectis BioScience P288ALS
VERSION 1.0 NOV 12, 2024		

	
will be imputed by the worst value (i.e. 0).
 
-Missing data due to drop-outs or withdrawal will be replaced by multiple imputation assuming Missing at random and monotone regression. Note: model for multiple imputation will be done without patient who died before V4.
 
Imputed values will be rounded to the nearest integer.

Population-level summary measure	Analysis approach

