5.11.2.2 Sensitivity analyses

Sensitivity analysis #1 considering estimand #2:

The same analysis proposed for the primary analysis will be provided for estimand #2

Sensitivity analysis #2 considering estimand #3:

The same analysis proposed for the primary analysis will be provided for estimand #3.

Missing data due to death whatever the cause: the ALSFRS-R score at month 6 will be imputed by the worst value (i.e. 0).

For the MAR multiple imputation part, the model used for imputation will be done without patients who died before V4.

First step (if necessary):

If the missing pattern is not monotone (missing values at month 3 and not at month 6), a first step will use the Markov Chain Monte Carlo (MCMC) method to impute data only partially to obtain a dataset with monotone missingness as proposed by O'Kelly, Michael; Ratitch, Bohdana. Clinical Trials with Missing Data: A Guide for Practitioners (Statistics in Practice), Wiley.

This first step assumes data are missing at random to impute intermittent (non- monotone) missing data using MCMC method with single chain, non-informative prior, 200 burn-in iterations, 50 iterations between imputations in a chain and Expectation-Maximization algorithm (using mcmc chain=single impute=monotone prior = jeffreys options) and seed of xxxxx.

The imputation model will be fitted **by treatment** and will include the following terms in this specific order:

- ALSFRS total scores in order: at baseline, Month 3 and Month 6

Note: imputed values will be rounded to the nearest integer.

Second step:

STATISTICAL ANALYSIS PLAN		
InFlectis BioScience	Sponsor:	InFlectis BioScience
	Protocol Number:	P288ALS
VERSION 1.0 NOV 12, 2024		

If step 1 is necessary, the output data set from Imputation Model Step 1 will be the input for Step 2 using Monotone Regression. The second imputation model will generate one imputation for each of previous multiply imputed datasets of MI1 (i.e. by _Imputation_) and a seed of yyyy. The model will include only the following variables:

- Randomized Treatment (as a classification variable)
- ALSFRS total scores in order: at baseline, Month 3 and Month 6

If step 1 is not necessary, the imputation model will use monotone regression and generate 50 imputations and a seed of 293654. The model will include only the following variables:

- Randomized Treatment (as a classification variable)
- ALSFRS total scores in order: at baseline, Month 3 and Month 6

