7 CHANGES TO PLANNED PROTOCOL ANALYSIS

Changes to planned protocol analysis are the following:

- Modification of the primary analysis of the primary efficacy endpoint. Modification of the imputation method for missing data due to deaths occurring during the study. The ANCOVA model will be used instead of the MMRM to account for different sources of missing data.
- Deletion of the Bayesian analysis. A Bayesian analysis was planned in the protocol to combine prior data from literature (Promise study) with current study data. However, as the populations differ (all-comers ALS patients in the Promise study vs bulbar-onset ALS patients only in P288ALS study), this Bayesian analysis will be further considered in a *post hoc* manner if appropriate.

STATISTICAL ANALYSIS PLAN		
InFlectis BioScience	Sponsor:	InFlectis BioScience
	Protocol Number:	P288ALS
VERSION 1.0 NOV 12, 2024		

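### For ALSFRS-R at Month 6, the SAP drops the protocol's pattern-mixture analysis of withdrawals in favour of a missing-at-random imputation, and does not declare the change

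*Protocol*

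**What the plan says.** Protocol 8.1.5.2 (and the synopsis) plans a mixed model for the ALSFRS-R change that is valid under missing at random (MAR). It then concedes that "the MAR assumption is untestable and may not hold for subjects withdrawing at their own will". For that reason it adds that "a sensitivity analysis will be based on a pattern mixture model that uses a multiple imputation technique analysed with an ANCOVA" and leaves the detail to the next document: "The imputation model will be further clarified in the SAP".

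SAP 2.3, Table 1, defines three strategies for Month 6:

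- **Estimand #1 (primary).** "Missing data due to drop-outs or withdrawal will be imputed with the same approach used for handling missing data due to deaths for reasons" unrelated to progression. If Month 3 is observed, the patient's own baseline-to-Month-3 line is extended to day 180. If not, the value is predicted from baseline by a regression fitted in the patient's own arm.
- **Estimand #2.** Drop-outs are treated as in #1. Only the scoring of deaths changes.
- **Estimand #3.** "Missing data due to drop-outs or withdrawal will be replaced by multiple imputation assuming Missing at random and monotone regression".

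SAP 5.11.2.2 (Sensitivity analyses) repeats the label for Estimand #3: "For the MAR multiple imputation part, the model used for imputation will be done without patients who died before V4". Its second step regresses on randomised treatment and the baseline, Month 3 and Month 6 scores.

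SAP section 7 opens with "Changes to planned protocol analysis are the following". It names the change of primary analysis, with ANCOVA in place of the mixed model and a new imputation for deaths, and the removal of the Bayesian analysis.

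**The concern.** The promised analysis had one purpose: to show what happens to the ALSFRS-R result if people who choose to leave fare worse than their observed data suggest. The SAP keeps the outer form, multiple imputation followed by ANCOVA, but imputes under the very assumption that the protocol doubted. Section 7 neither lists nor justifies this.

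It matters more here because Table 1 declares a treatment-policy strategy, while Protocol 5.3 states that nothing further is collected once a patient has withdrawn. The imputation has to stand in for all later outcomes of those patients. If withdrawals are more frequent on IFB-088 and go worse than projected, the planned analyses would agree with one another and all favour the drug.

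**Working it through.** **1. What each ALSFRS-R analysis allows a withdrawn patient to do**

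| Analysis | Source of the Month 6 value | Can it be worse than own scores or own arm predict? |
|---|---|---|
| Estimand #1 | Own slope, or own-arm regression | No |
| Estimand #2 | Same as #1 | No |
| Estimand #3 | MAR regression with treatment in the model | No |
| Per-protocol, Hodges-Lehmann, subgroups (5.11.2.2.3, .4, .6) | Reuse #1 | No |

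No delta, reference-based, tipping-point or other pattern-specific term appears in SAP 2.3 or 5.11.2.2.

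**2. Inputs for size**

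The plan states no figure for this analysis. Its drop-out figure reproduces: 42 / 0.85 = 49.4, rounded up to 50. At 2:1, 50 patients split about 33:17.

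The documents give no SD of ALSFRS-R change, no withdrawal rate by arm and no excess decline. Assumed: SD 4 to 8 points; excess decline 2 to 6 points; all of a 15% drop-out on IFB-088 (0.15 × 33 ≈ 5) lacking Month 6 data; no excess on placebo.

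**3. Shift in the treatment difference**

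Shift = drop-out share × excess decline:

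- 2 points: 0.15 × 2 = 0.30
- 4 points: 0.15 × 4 = 0.60
- 6 points: 0.15 × 6 = 0.90

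SE = SD × √(1/33 + 1/17) = SD × 0.2985:

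- SD 4: SE 1.19, so 0.60 / 1.19 = 0.50 SE
- SD 8: SE 2.39, so 0.60 / 2.39 = 0.25 SE

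Over the whole assumed range the shift runs from 0.30 / 2.39 = 0.13 SE to 0.90 / 1.19 = 0.75 SE.

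**4. Simulation of the planned rules**

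The set-up is 33:17 patients and 2,500 trials per row. Mean decline is 1 point per month (slope SD 0.6, measurement SD 1.2). Month 3 is always observed, and withdrawals lose Month 6. There is no drug effect other than the assumed excess decline, which applies to withdrawals in both arms. The last column subtracts the same excess from imputed IFB-088 values only. Entries are the mean difference, IFB-088 minus placebo.

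| Withdrawal, IFB-088 / placebo | Excess | Complete data | Estimand #1 | Estimand #3 | Delta on IFB-088 only |
|---|---|---|---|---|---|
| 20% / 5% | 0 | -0.05 | -0.04 | -0.05 | -0.05 |
| 20% / 5% | 3 | -0.49 | -0.03 | -0.04 | -0.64 |
| 20% / 5% | 6 | -0.87 | +0.03 | +0.03 | -1.18 |
| 22.5% / 0% | 6 | -1.35 | 0.00 | 0.00 | -1.36 |
| 15% / 15% | 6 | 0.00 | +0.02 | +0.02 | -0.89 |

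In the third row, one-sided rejection at 0.10 in favour of IFB-088 is 10.6% (Estimand #1) and 10.9% (Estimand #3), against 2.3% with complete data. The two planned analyses agree and neither shows the departure. In the last row there is no bias to find. There the one-arm delta gives -0.89 although the true difference is zero, so it is a stress test and not a correction.

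**The case against.** The other side has several sound points.

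- **Rules outside MAR do exist.** A reader might infer that nothing in the plan departs from MAR. That is not so: MITOS and King's count every missing Month 6 value as progression (SAP Tables 2 and 3), and ALSFRS-R is scored 0 for some or all deaths. These rules cover other endpoints or deaths, not ALSFRS-R in patients who withdraw.
- **Own-slope extrapolation is not a MAR model.** It is a deterministic single imputation. It is tempting to say that all three estimands treat an IFB-088 drop-out as still benefiting, but a patient who declined fast before Month 3 is projected to go on doing so. Nor is agreement between the estimands empty, since it speaks to dependence on the imputation method. It does not speak to withdrawals who do worse than projected.
- **Some drop-outs will have data.** ALSFRS-R is measured at the premature discontinuation visit (Protocol 4.1.9), and SAP 5.2.5 counts that visit as V3 on days 83-99 or V4 on days 170-194. This reduces the problem. The imputation rules make no use of a value at, say, day 130.
- **The protocol named no method.** It promised a pattern-mixture model, not a delta or reference-based one, so those are choices among options. A model labelled and built as MAR still does not meet the promise.
- **Stakes are limited.** Safety is primary; efficacy is unpowered estimation at two-sided 0.20.

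None of this restores the missing analysis or the missing entry in section 7.

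**Conclusion.** The point holds for the Month 6 ALSFRS-R change in patients who withdraw. The protocol's planned safeguard against failure of MAR is absent from the SAP, and its loss is undeclared. Because MAR cannot be tested from the data, what is missing is a stress test.

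The size is illustrative: about 0.6 point, or 0.25 to 0.50 SE, for a 4-point excess in 15% of IFB-088 patients and none on placebo, over an SD of 8 down to 4. It also assumes that the whole 15% are withdrawals without Month 6 data; the documents do not say whether deaths are included. With equal withdrawal and equal excess decline in both arms the bias is nil.

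A reader might also infer that imputing IFB-088 drop-outs from placebo would cut any effect by 15%. That is an upper figure, reached only if drop-outs lose the whole effect. If the model conditions on an observed Month 3 score, the effect grows linearly and the Month 3 coefficient is near 1, about half is retained and the cut is nearer 0.15 × 0.5 = 7.5%.

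This should be corrected because it concerns the protocol's own commitment. It does not touch the primary safety objective.

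**What to change.** In SAP 5.11.2.2 keep the MAR imputation for Estimand #3, which is the closest remaining link to the protocol's mixed model. Pair it with at least one of:

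1. **Delta-adjusted tipping point.** Subtract 0 to 6 points from imputed Month 6 values of IFB-088 withdrawals and report where the conclusion changes. The upper end equals six months at the average decline of about one point per month given in Protocol 4.2.2.1. Present it as a bound, since a one-arm delta overstates the bias when placebo withdrawals decline too.
2. **Placebo-reference imputation.** Fit the second-step model to placebo patients and apply it to IFB-088 withdrawals.

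Pool either one over the 50 imputations as already described in the third step. Add an entry to SAP section 7 stating that the protocol's pattern-mixture analysis has been changed, and why. If the database is already locked, SAP section 5 provides for an addendum.

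The cost is one or two more sensitivity results and a modest change to imputation code that is already planned. The placebo reference will be imprecise, resting on about 17 randomised patients (14 evaluable in the protocol's planning).
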